Analysis plan for Specific Aim 1. Prior to conducting our multivariable analyses, we will examine study variables using descriptive statistics, testing for differences across demographic characteristics (e.g., race/ethnicity, age) using t-tests, ANOVAs, and Chi-squares, as appropriate. Systematic baseline differences are not expected; however, any parameters that differ across conditions at baseline will be included as covariates in subsequent models. We will calculate descriptive summary statistics corresponding to study variables at each follow-up (FU) to understand any temporal patterns, as well as compare the two groups in terms of average change from baseline to 12-months post-baseline. We will use the general framework of generalized linear models (GLM) to model the longitudinal outcome trajectories and GEE method to account for within-subject correlation across the four time points (baseline, 3-, 6-, and 12-months). Stratified randomization of participants to the groups based on their gender requires that the analysis also include gender as covariate. The general form of the analysis model will be $g(\mu) = \alpha_0 + \alpha_1 X + \beta I + \sum \gamma_i T_i + \sum \delta_i T_i I$, where g denotes the link function (identity for continuous outcome, logit for binary outcome and natural log for count outcomes) X represents the indicator of female (vs. male), I is the group indicator for Link2CARE (vs. SOC), and T_i is the indicator for time at 3-month, 6-month, and 12-month evaluation (vs. baseline) for $i=1, 2, \text{ and } 3$. The interaction coefficients δ_i are of interest, measuring the difference in the rate of change in outcome across the two treatment groups at each follow-up assessment. We will employ the above analytic approach to examine differences between youth in Link2CARE and in the SOC condition with respect to key study parameters within these four domains detailed below. Proposed hypotheses are that the experimental arm (Link2CARE) would have better outcomes (e.g. greater reduction on total number of unprotected anal and vaginal sex occasions in past three months from baseline to 12 month FU; greater increase in proportion of acceptance of HIV testing at initial offering; greater reduction on frequency of substance use in past 30 days at 3-, 6- and 12-month FUs; and of those referred to SU treatment, a greater number of youth attending intake plus one treatment session at 3-, 6- and 12-month FUs)

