
Analysis of participant attrition and missing data. We will make every effort to retain participants in the study to avoid bias due to attrition. For those individuals who refuse continued participation, we will document reasons for study discontinuation and Rubin's multiple imputation method with 11 repeated imputations will be

employed to impute the missing endpoint for conducting the intent-to-treat analysis.

QUALITY ASSURANCE

Procedures in place to ensure the validity and integrity of the data

All data collection protocols include a form on which research staff members record any problems with the data collection or unusual occurrences during the collection. They also are encouraged to bring problems to the attention of the Project Director, or PI. These members of the research staff also meet on a regular basis to identify and address any issues that arise. These procedures allow our research staff an opportunity to quickly review and respond to any possible concerns. We expect missing data to be minimal, nevertheless regular (quarterly) quality assurance checks will be made by the Project Director to identify any systematic missing information and remedies will be enacted.

Procedures to guarantee the accuracy and completeness of the data, during data collection, entry, transmission, and analysis.

To check for errors in data entry, we will adhere to the following protocol. All face-to-face surveys will be recorded. One out of every seven recordings for each interviewer will be compared to the entered interview. If we identify a proportion of errors that is more than 1% error, we will temporarily suspend the interviewer from active interviewing. We will listen to all interviews for comparison purposes, identifying any errors and will re-train the interviewer to ensure accuracy and completeness of all face-to-face survey interviews. A subset (10%) of all data from hard-copy/paper-pencil instruments that is entered into the project database will be similarly checked. If we identify a proportion of errors that is more than 1% error, we will reenter all questionnaires and subsequently compare both data sets. We will go back to the original surveys to resolve all inconsistencies. To prevent data entry problems we will prepare a data entry system that will alert us when data are entered that are out of range.

Procedures for preventing and addressing breaches of confidentiality

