Only two of the three co-primary endpoints will be monitored for early stopping: (1) total number of unprotected anal and vaginal sex occasions in past three months at 12 month FU; (2) any HIV testing between 6-month and 12-month FU (y/n). We will follow a modified Haybittle-Peto rule⁷ to propose early stopping as follows: the z-score for testing the null hypothesis for each of the two primary outcomes will be calculated once during interim analyses (see below) when one-quarter of the expected total 12-month outcome data has been observed (after approximately 6-months of 12-month data collection). This will allow the PSMB to recommend continuing to recruit subjects or stop the trial for strong positive or negative efficacy prior to the end of subject recruitment.

The z-score for early stopping will be $Z = 3.6623$ for either monitored outcome, corresponding to a normal two-tailed critical value cutting off nominal probability 0.00025 in each tail. It follows that either endpoint may suggest early stopping with total two-tailed probability 0.0005 under the null hypothesis and therefore the probability of early stopping under the null hypothesis for either endpoint in either direction will be no greater than 0.001. This stopping rule is less conservative than an O'Brien-Fleming-like alpha spending function monitoring plan, yet is still sufficiently conservative to leave the terminal significance criteria nearly unaffected. In particular, assuming no early stopping, if either of the two monitored co-primary endpoints specified above possesses the smallest P -value among all three co-primary endpoints, the group comparison will be declared significant at the 0.05 level (adjusted for multiple comparisons) if the terminal z-score criterion is $Z = 2.3978$ or greater. This Z -score is very close to the nominal $0.05/3 \approx 0.01667$ two-tailed normal critical value of 2.3940, which is the initial required criterion under the Holm step-down procedure without sequential monitoring. If the unmonitored co-primary endpoint (acceptance of HIV testing at initial offering, y/n) should have its P -value as smallest and less than or equal to $0.05/3 \approx 0.01667$, then it will be declared significant (at the two-tailed 0.05 level, adjusted for multiple comparisons).

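### The interim stopping rule puts a normal cut-off on a likely skewed count at about 42 per arm, so the stated false-stop bound of 0.001 can be exceeded; the effect on the final 0.05 level is modest.

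*Combined protocol and SAP*

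**What the plan says.** Trial Stopping Rules provides for one efficacy look, taken "when one-quarter of the expected total 12-month outcome data has been observed". Two co-primary endpoints are monitored: the three-month count of unprotected sex occasions at 12 months, and any HIV test between 6 and 12 months. The boundary is given as follows: "The z-score for early stopping will be $Z = 3.6623$ for either monitored outcome, corresponding to a normal two-tailed critical value". It is described as a "normal two-tailed critical value cutting off nominal probability 0.00025 in each tail". From this the section concludes that "the probability of early stopping under the null hypothesis for either endpoint in either direction will be no greater than 0.001". For a monitored endpoint with the smallest P-value, the first Holm step at the end uses Z = 2.3978, in place of 2.3940 without monitoring.

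Analysis plan for Specific Aim 1 specifies GEE over four visits, with link functions "logit for binary outcome and natural log for count outcomes". The group-by-time interaction is the contrast of interest, and familywise error is held at 0.05. For missing endpoints in the intent-to-treat analysis, "Rubin's multiple imputation method with 11 repeated imputations will be" used.

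The plan does not name a variance estimator, a small-sample correction, a t or permutation reference, or the exact statistic behind the interim z. It does not say whether imputation applies at the interim.

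**The concern.** The 0.001 bound is stated without qualification, but it follows only if the statistic is normal far into the tail. The count is likely to be skewed with many zeros, because Table 1 requires only lifetime unprotected sex while the endpoint covers three months. With about 42 per arm, a sandwich standard error for such a count tends to be too small. The relative error in the tail probability is greatest far out, which is where a 3.66 boundary sits.

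At stake is a recommendation to end a 450-person trial on about 84 observations because of a chance crossing. A smaller matter is whether the final first-step criterion for this endpoint has its stated size.

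**Working it through.** **Inputs from the documents.** Expected 12-month sample 338, or 169 per arm (Sample size and power); look at one quarter; boundaries 3.6623 and 2.3978; log-link GEE interaction; 11 imputations; 25% attrition. The interim sample is 338/4 = 84.5, about 42 per arm.

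**The plan's own figures.**
- Normal quantiles: z(1 − 0.00025) = 3.4808 and z(1 − 0.000125) = 3.6623. So 3.6623 cuts off 0.000125 per tail, or 0.00025 two-tailed. The nominal either-endpoint bound is 2 × 0.00025 = 0.0005, half the stated 0.001.
- Solving P(|Z1| > 3.6623 or |Z2| > c) = 0.05/3 with correlation √0.25 = 0.5 gives c = 2.3978, as stated. With 3.4808 instead, c would be 2.4021. The final cut-off therefore matches 3.6623, not the verbal tail probability.
- The nominal two-sided P at 2.3978 is 0.0165.

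**Assumptions, because the documents give none.** Mean 10, no effect, complete data, sandwich variance, baseline-to-12-month interaction on the log scale, no gender term. The statistic is the difference between arms in log(m1/m0), where m0 and m1 are an arm's baseline and 12-month means. Its variance is the sum over arms of Σ(y1/m1 − y0/m0)²/n². Within-person correlation is 0.2 to 0.8.

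**Interim, 42 per arm, P(|z| > 3.6623) for the count alone.** Runs per cell were 300,000 (500,000 for k = 1). The coefficient of variation is √(1/10 + 1/k) for negative binomial counts and √(1/10 + exp(sd²) − 1) for Poisson-lognormal counts.

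| Distribution | CV | False-stop rate |
|---|---|---|
| Negative binomial k = 1 | 1.05 | 0.0006 (correlation 0.5) |
| k = 0.5 | 1.45 | 0.0004–0.0010 |
| k = 0.25 | 2.02 | 0.0003–0.0015 |
| k = 0.1 | 3.18 | 0.0005–0.0039 |
| Poisson-lognormal sd 1.0 | 1.35 | 0.0013–0.0016 |
| sd 1.25 | 1.97 | 0.0019–0.0028 |
| sd 1.5 | 2.93 | 0.0029–0.0063 |

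A repeat simulation gave 0.0002–0.0041 (negative binomial) and 0.0012–0.0065 (Poisson-lognormal). The nominal rate is 0.00025 and the stated per-endpoint rate is 0.0005.

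**Either endpoint.** The binary endpoint adds at most 0.0003. With negative binomial counts and correlation 0.5, the combined rate is about 0.0008–0.0009 for k 0.2 to 1, inside the bound, and 0.0020 at k = 0.1. In every Poisson-lognormal cell the count alone exceeds 0.001.

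**Choice of statistic.** At k = 0.3 and correlation 0.5, the interaction gives 0.0007 and a contrast of 12-month values only gives 0.0018. The unnamed statistic therefore matters.

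**Final look, 169 per arm, P(|z| > 2.3978).** About 0.015–0.023 (negative binomial) and 0.021–0.031 (Poisson-lognormal), against 0.0165. Simulated familywise error under the global null, interim included, is 0.050–0.056 for negative binomial counts with k 0.1 to 1 (Monte Carlo SE about 0.001). A rough figure for Poisson-lognormal counts, taking the three final tests as independent, is 1 − (1 − p)(1 − 0.0165)(1 − 0.01667). This gives 0.053 at p = 0.021 and 0.063 at p = 0.031.

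**Pooling alone.** With m = 11 and 25% missing information, Rubin's degrees of freedom are 10/0.25² = 160 and P at 2.3978 is 0.0176. Over 10% to 30% missing information, with small-sample degrees of freedom, the range is about 0.017–0.019.

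**The case against.** The strongest reply is that the boundary has slack. Since 3.6623 is nominally 0.00025 two-tailed, it is twice as strict as the promised 0.0005. A t reference with 82 degrees of freedom gives 0.00044 at 3.6623, still inside the promise. With moderate negative binomial overdispersion the combined false-stop rate also stays below 0.001. All of this stands. The slack covers mild cases but not Poisson-lognormal skew, heavy overdispersion, or, at k = 0.25, low within-person correlation.

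The sandwich variance and the skew are assumptions, and that also stands. A model-based Poisson variance would do worse for overdispersed counts, however, and the plan's silence leaves the bound without support.

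A reader might infer four stronger things that the documents do not support:
- That the 0.05 familywise level is seriously broken. For the specified interaction and negative binomial counts the excess is at most about 0.006.
- That imputation distorts the interim z. The plan does not say that imputation applies there, and at the end Rubin's method ordinarily brings its own t reference.
- That the mislabelled tail probability is anti-conservative. It is conservative.
- That crossing the boundary ends the trial. The rule only proposes stopping, and the monitoring board may ask for more information before it recommends.

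**Conclusion.** The point holds in limited form. Trial Stopping Rules promises a false-stop bound that its normal cut-off does not guarantee for the count endpoint at about 42 per arm. Whether and by how much the bound is missed depends on a distribution the documents do not give. For the count alone the range runs from below the stated 0.0005 to about 0.006, with the breach clear for lognormal-type skew and small or absent for moderate negative binomial overdispersion. The sentence also contradicts itself by a factor of two, in the conservative direction. The final-look effect is modest. This should be settled before the interim, but it does not undermine the design.

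**What to change.** 1. Reconcile 3.6623 with its stated tail probability and write the interim criterion as a two-sided P-value per endpoint. P = 0.00025 keeps both 3.6623 and 2.3978. P = 0.0005 keeps the stated probabilities but corresponds to 3.4808 and a final value of 2.4021.
2. Name the interim statistic, its contrast and its variance estimator, and say whether imputation is used at the interim.
3. For the count at the interim, take P from a re-randomization test that permutes arm within gender strata and uses the studentized GEE statistic on observed data. With 100,000 permutations, the Monte Carlo error at P = 0.00025 is √(0.00025/100,000) ≈ 0.00005. The test controls error under the sharp null that arm affects neither the count nor dropout. A t correction is simpler but less secure. With critical value 3.830 and an n/(n − 1) variance correction, the negative binomial rate for k 0.2 to 1 falls to about 0.0001–0.0006 for the interaction but only to 0.0004–0.0017 for a contrast of 12-month values.
4. At the final analysis, use a small-sample-corrected sandwich standard error with Rubin's t reference, and give a re-randomization P-value as a sensitivity check. Repeating the imputation inside every permutation is not required.

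The cost is SAP wording, computing time and a slightly harder stopping criterion for the count. No change to sample size or data collection is needed.

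### The interim boundary Z = 3.6623 cuts off 0.000125 in each tail, not the stated 0.00025; the two-tailed figure per endpoint is doubled in the same way

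*Combined protocol and SAP*

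**What the plan says.** Under Trial Stopping Rules, two of the three co-primary endpoints are monitored with a modified Haybittle-Peto rule. There is a single look, "when one-quarter of the expected total 12-month outcome data has been observed". The boundary is given as a Z value and translated into a tail area in the same sentence: Z = 3.6623 "for either monitored outcome, corresponding to a normal two-tailed critical value cutting off nominal probability 0.00025 in each tail".

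The next sentence builds on that area. It says that "either endpoint may suggest early stopping with total two-tailed probability 0.0005 under the null hypothesis", and concludes that the chance of stopping early under the null "for either endpoint in either direction will be no greater than 0.001".

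For the final analysis, a monitored endpoint with the smallest P-value of the three is declared significant "if the terminal z-score criterion is $Z = 2.3978$ or greater". This is compared with the unmonitored "two-tailed normal critical value of 2.3940, which is the initial required criterion under the Holm step-down procedure without sequential monitoring".

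The rest of Trial Stopping Rules, Plans for Interim Analysis of efficacy data, and Monitoring activities all return to the interim look, but none restates or corrects the probabilities.

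**The concern.** The Z value and the tail area in one sentence do not belong together. A boundary of 3.6623 and a boundary with 0.00025 in each tail are different rules, so the paragraph defines the boundary in two incompatible ways. An interim statistic between 3.4808 and 3.6623 would cross under the stated probability but not under the stated Z.

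This is the trial's only efficacy stopping rule, and the monitoring board is to be told whether it has been met. Anyone who programs the rule from P-values would apply a different boundary from someone who programs it from Z. The later Holm steps call for P-values adjusted for the interim look. That adjustment uses the interim boundary, so a wrong tail area could be carried into it.

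**Working it through.** **Inputs, all from Trial Stopping Rules:** interim boundary 3.6623; stated area 0.00025 per tail, 0.0005 two-tailed per endpoint, at most 0.001 over both; two monitored endpoints; one look at information fraction t = 0.25; first Holm level 0.05/3 = 0.01667 two-tailed; nominal critical value 2.3940; terminal value 2.3978.

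**Step 1. The plan's chain of probabilities.** 2 × 0.00025 = 0.0005 per endpoint, and 2 × 0.0005 = 0.001 over two endpoints. The doubling is done correctly; the question is whether the starting figure fits Z = 3.6623.

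**Step 2. Tail area at the printed boundary**, with Φ the standard normal distribution function.

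| Quantity | Formula | True value | Stated |
|---|---|---|---|
| Each tail | 1 − Φ(3.6623) | 0.00012498 | 0.00025 |
| Two-tailed, one endpoint | 2 × 0.00012498 | 0.00024996 | 0.0005 |
| Upper bound, two endpoints | 4 × 0.00012498 | 0.00049992 | 0.001 |

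The inverse check agrees: an upper-tail area of 0.000125 gives Z = 3.66226, and 0.00025 gives Z = 3.48076. The figure 0.00025 is therefore the two-tailed total at 3.6623, labelled as the area in each tail.

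**Step 3. Probability that either endpoint crosses under the null**, by the correlation between the two interim statistics (the plan gives none, so a range is shown):

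| Correlation | 0 | 0.2 | 0.5 | 0.8 | 1 |
|---|---|---|---|---|---|
| P(either crosses) | 0.00049986 | 0.00049951 | 0.00049360 | 0.00045134 | 0.00024996 |

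The stated bound of 0.001 holds throughout, but is about 2 to 4 times the actual probability.

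**Step 4. Which figure is wrong, the Z or the probability?** The nominal value reproduces: the upper 0.05/6 point of the normal is 2.39398, printed as 2.3940. For the terminal value c after an interim boundary b, solve

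P(|Z1| ≥ b) + P(|Z1| < b, |Z2| ≥ c) = 0.05/3,

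where Z1 and Z2 are the interim and final statistics, with correlation √t = √0.25 = 0.5.

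| Information fraction | c for b = 3.6623 | c for b = 3.48076 |
|---|---|---|
| 0.20 | 2.39821 | 2.40279 |
| 0.25 (as planned) | 2.39782 | 2.40209 |
| 0.30 | 2.39741 | 2.40135 |

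The printed 2.3978 matches b = 3.6623 at the planned quarter to four decimals. The alternative boundary does not reach 2.3978 anywhere in this range.

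**Step 5. Type I error of a monitored endpoint at the first Holm step, t = 0.25.** With 3.6623 then 2.3978 the total is 0.016668, against a target of 0.016667. With 3.4808 then 2.3978, the mixture that results if the interim is run from the stated probability, it is 0.01686.

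**The case against.** The strongest reply is that nothing operational turns on this. The interim rule and the first terminal criterion are both set in Z, so the probabilities only describe the rule. Even the worst misuse moves the error from 0.01667 to 0.01686. That stands, and it is why the point is minor. It is also a single slip, since the second wrong figure is the first one doubled.

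The conclusion that the paragraph draws, a null stopping probability of at most 0.001, is true. That stands too: the bound is loose, not false, and tightening it is optional.

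A third reply concerns intent. The authors may have begun from a round total of 0.001 and halved once too often when looking up Z, which would make the boundary the slip. Agreement among the Z values cannot prove what was intended. But the terminal value was evidently computed from 3.6623, so on that reading two Z values would have to change. An information fraction of 0.50 would bring the terminal value for 3.4808 to 2.39808, near the printed figure, but it contradicts the stated look at one-quarter. The documents support keeping the Z values.

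Finally, the error calculation covers a monitored endpoint at the first Holm step only. The adjusted P-values at the later steps were not computed here.

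**Conclusion.** The concern holds, at minor severity. Two stated probabilities are wrong for Z = 3.6623, each by a factor of two: 0.00025 per tail should be 0.000125, and 0.0005 two-tailed per endpoint should be 0.00025. The misstatement is conservative, because early stopping under the null is half as likely per endpoint as the text says. The three printed Z values are mutually consistent, and the printed pair keeps the first-step error on target.

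The tail areas need only the normal distribution that the plan itself invokes. The terminal-value check also assumes the usual independent-increments correlation √t, and its conclusion is unchanged for information fractions from 0.20 to 0.30.

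**What to change.** Keep the interim Z of 3.6623 and the terminal Z of 2.3978. In Trial Stopping Rules, change the area in each tail from 0.00025 to 0.000125, and the two-tailed probability per endpoint from 0.0005 to 0.00025. Optionally tighten the bound over both endpoints from 0.001 to 0.0005.

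The cost is two corrected figures in one paragraph and one optional tightening. No boundary, sample size, analysis or procedure changes, and no other section needs editing.
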